10.2 General statistical methods

The data will be summarized with respect to demographic and baseline characteristics, efficacy observations and measurements, and safety observations and measurements. Primary efficacy and safety/tolerability analysis will be conducted at 15 months of median follow up time, i.e. at approximately two times the median PFS reported in the BOLERO-2 study (Baselga et al. 2012; Yardley D. et al. 2014). Categorical variables will be summarized by absolute and relative frequencies. Continuous variables will be summarized by descriptive statistics (number of valid and missing observations, mean, standard deviation, median, minimum, and maximum).

Time to event data including rates of affected patients will be assessed using the Kaplan-Meier method. Two-sided 95% confidence intervals will be provided for the main statistical estimators.

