10.5 Primary objective

The primary objective is to evaluate the safety and tolerability profile of everolimus in post-menopausal women with ER positive, HER2 negative locally advanced or metastatic breast cancer after documented recurrence or progression following a non-steroidal aromatase inhibitor therapy in emergent growth markets (EGM).

The assessment of safety and tolerability will be based mainly on the frequency of adverse events, including the laboratory values that qualify as adverse events. Other safety data (e.g. vital signs, and special tests) will be considered as appropriate. The analysis will be descriptive. For all safety/tolerability analyses, the safety set will be used.

Data collected by AE CRFs will be coded using the MedDRA dictionary. The incidence of treatment-emergent adverse events (new or worsening from baseline) will be summarized by MedDRA system organ class and preferred term using frequency distributions. Additionally, AE will be summarized by maximum severity (based on CTCAE grades), and for AE with suspected drug relation, serious AE (SAE), and AE leading to permanent discontinuation of study drug. All information pertaining to AE noted during the study will be listed by patient, detailing the verbatim term given by the investigator, MedDRA preferred term and system organ class, start/end dates, severity, seriousness, relationship to study drug and action taken.

[figure not shown]
The AE onset will also be shown relative (in number of days) to the date of initial dose. AE starting more than 30 days after discontinuation of study drug will not be considered as treatment-emergent and will not be included in AE summary tables but listed only.

Data from other tests (e.g., electrocardiogram or vital signs) will be summarized descriptively as appropriate. Notable values will be flagged, and any other information collected will be listed as appropriate.

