Changes in patient's condition (investigator's discretion)	xx (xx.x)	NA	xx (xx.x)	NA	xx (xx.x)	NA

	Asian (N=xx)		Non-Asian (N=xx)		Total (N=xxx)	
	Everolimus (N=xxx)	Exemestane (N=xxx)	Everolimus (N=xxx)	Exemestane (N=xxx)	Everolimus (N=xxx)	Exemestane (N=xxx)
Need for other types of anticancer therapy (excluding palliative radiation for bone lesions)	xx (xx.x)	NA	xx (xx.x)	NA	xx (xx.x)	NA
Everolimus dose interruption > 4 wks	xx (xx.x)	NA	xx (xx.x)	NA	xx (xx.x)	NA
Other	xx (xx.x)	NA	xx (xx.x)	NA	xx (xx.x)	NA

NA: Not applicable SD: Standard deviation.

Asian: Indonesia, India, Vietnam, Turkey, South Korea, Thailand, Malaysia, Taiwan or Jordan.

Non-Asian: Australia, Morocco, South Africa or Tunisia.

^a Days with a zero dose level due are to temporary interruptions caused by safety reasons or patients' non-compliance.

^b Study treatment discontinuation refers to a patient's withdrawal from everolimus.

Table 6.1 Summary Overview of All Treatment-Emergent Adverse Events Summary, Any CTCAE Grade Overall and in Asian Subgroup - Safety Set

Adverse Event	Asian (N=xx)	Non-Asian (N=xx)	Total (N=xxx)
Number of patients, n (%)			
With no TEAE	xx (xx.x)	xx (xx.x)	xx (xx.x)
With at least one TEAE	xx (xx.x)	xx (xx.x)	xx (xx.x)
With at least one drug-related TEAE ^a	xx (xx.x)	xx (xx.x)	xx (xx.x)
With at least one serious TEAE	xx (xx.x)	xx (xx.x)	xx (xx.x)
TEAE leading to death	xx (xx.x)	xx (xx.x)	xx (xx.x)
Non-fatal serious TEAE	xx (xx.x)	xx (xx.x)	xx (xx.x)
With at least one serious drug-related TEAE, n (%)	xx (xx.x)	xx (xx.x)	xx (xx.x)
AE leading to death	xx (xx.x)	xx (xx.x)	xx (xx.x)
Non-fatal serious TEAE	xx (xx.x)	xx (xx.x)	xx (xx.x)
TEAE leading to treatment discontinuation, n (%)	xx (xx.x)	xx (xx.x)	xx (xx.x)
With at least one treatment-emergent AESI, n (%)	xx (xx.x)	xx (xx.x)	xx (xx.x)

Asian: Indonesia, India, Vietnam, Turkey, South Korea, Thailand, Malaysia, Taiwan or Jordan.

Non-Asian: Australia, Morocco, South Africa or Tunisia.

TEAE: Treatment emergent adverse event. TEAE are defined as any adverse event with a start date on or after the date of the first dose of study drug and within 30 days of treatment discontinuation. AESI = Adverse events of special interest.

Adverse events are coded using MedDRA version 19.1. AEs are assessed using CTCAE version 4.03.

Percentages are based on the number of patients in the Safety Set.

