TEAE	Safety Set (N=xxx)		Median time to resolution, weeks (95% CI) ^b
	Number of patients with Grade 3-4 Events	n (%) patients with event resolved ^a	
Stomatitis	xx	xx (xx.x%)	x.x (x.x, x.x)
Rash	xx	xx (xx.x%)	x.x (x.x, x.x)
Infection (including pneumonia)	xx	xx (xx.x%)	x.x (x.x, x.x)
Pneumonitis	xx	xx (xx.x%)	x.x (x.x, x.x)

CI: Confidence Interval.

TEAE: Treatment emergent adverse event. TEAE are defined as any adverse event with a start date on or after the date of the first dose of study drug and within 30 days of treatment discontinuation.

^a The denominator of percent of patients resolved is the number of patients with grade 3-4 events.

^b Median time to resolution based on Kaplan-Meier Estimates. Confidence intervals calculated when at least two patients have event resolved.

Table 6.14.1 Time to Resolution of Treatment-Emergent Adverse Event of Special Interest Associated with mTOR Inhibition, Grade 3-4: Asian vs. Non-Asian – Safety Set

TEAE	Asian (N=xxx)			Non-Asian (N=xxx)		
	Number of patients with Grade 3-4 Events	n (%) patients with event resolved ^a	Median time to resolution, weeks (95% CI) ^b	Number of patients with Grade 3-4 Events	n (%) patients with event resolved ^a	Median time to resolution, weeks (95% CI) ^b
Stomatitis	xx	xx (xx.x%)	x.x (x.x, x.x)	xx	xx (xx.x%)	x.x (x.x, x.x)
Rash	xx	xx (xx.x%)	x.x (x.x, x.x)	xx	xx (xx.x%)	x.x (x.x, x.x)
Infection (including pneumonia)	xx	xx (xx.x%)	x.x (x.x, x.x)	xx	xx (xx.x%)	x.x (x.x, x.x)
Pneumonitis	xx	xx (xx.x%)	x.x (x.x, x.x)	xx	xx (xx.x%)	x.x (x.x, x.x)

Asian: Indonesia, India, Vietnam, Turkey, South Korea, Thailand, Malaysia, Taiwan or Jordan.

Non-Asian: Australia, Morocco, South Africa or Tunisia.

CI = Confidence Interval.

TEAE: Treatment emergent adverse event. TEAE are defined as any adverse event with a start date on or after the date of the first dose of study drug and within 30 days of treatment discontinuation.

^a The denominator of percent of patients resolved is the number of patients with grade 3-4 events.

^b Median time to resolution based on Kaplan-Meier Estimates. Confidence intervals calculated when at least two patients have event resolved.

Table 6.15 Time to Resolution of Treatment-Emergent Adverse Event of Special Interest Associated with mTOR Inhibition, Grade 2-4 - Safety Set

This table will be created using the same layout as Table 6.14.

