Table 6.15.1 Time to Resolution of Treatment-Emergent Adverse Event of Special Interest Associated with mTOR Inhibition, Grade 2-4: Asian vs. Non-Asian: Safety Set

This table will be created using the same layout as Table 6.14.1.

Table 6.16 Time to Resolution of Recurrence After the First Episode of Treatment-Emergent Adverse Event of Special Interest Associated with mTOR Inhibition, Grade 3-4 - Safety Set

This table will be created using the same layout as Table 6.14.

Table 6.16.1 Time to Resolution of Recurrence After the First Episode Treatment-Emergent Adverse Event of Special Interest Associated with mTOR Inhibition, Grade 3-4: Asian vs. Non-Asian: Safety Set

This table will be created using the same layout as Table 6.14.1.

Table 6.17 Time to Resolution of Recurrence After the First Episode of Treatment-Emergent Adverse Event of Special Interest Associated with mTOR Inhibition, Grade 2-4 - Safety Set

This table will be created using the same layout as Table 6.14.

Table 6.17.1 Time to Resolution of Recurrence After the First Episode Treatment-Emergent Adverse Event of Special Interest Associated with mTOR Inhibition, Grade 2-4: Asian vs. Non-Asian: Safety Set

This table will be created using the same layout as Table 6.14.1.

Table 6.18 Time to onset of Treatment-Emergent Adverse Event of Special Interest Associated with mTOR Inhibition, Grade 2-4 - Safety Set

This table will be created using the same layout as Table 6.14.

Table 6.18.1 Time to onset of Treatment-Emergent Adverse Event of Special Interest Associated with mTOR Inhibition, Grade 2-4: Asian vs. Non-Asian: Safety Set

This table will be created using the same layout as Table 6.14.1.

Table 7.1.1 ECOG Performance Status Scores Overall and in Asian Subgroup - Full Analysis Set

Week	n	ECOG Performance Status ^a , n (%)					
		0	1	2	3	4	5
Total (N=XXX)							
Baseline	xx	xx (xx.x)	xx (xx.x)	xx (xx.x)	xx (xx.x)	xx (xx.x)	xx (xx.x)
Week 4	xx	xx (xx.x)	xx (xx.x)	xx (xx.x)	xx (xx.x)	xx (xx.x)	xx (xx.x)
Week 10	xx	xx (xx.x)	xx (xx.x)	xx (xx.x)	xx (xx.x)	xx (xx.x)	xx (xx.x)
Week 20	xx	xx (xx.x)	xx (xx.x)	xx (xx.x)	xx (xx.x)	xx (xx.x)	xx (xx.x)
Week 30	xx	xx (xx.x)	xx (xx.x)	xx (xx.x)	xx (xx.x)	xx (xx.x)	xx (xx.x)
Week 40	xx	xx (xx.x)	xx (xx.x)	xx (xx.x)	xx (xx.x)	xx (xx.x)	xx (xx.x)
Week 50	xx	xx (xx.x)	xx (xx.x)	xx (xx.x)	xx (xx.x)	xx (xx.x)	xx (xx.x)
:	xx	xx (xx.x)	xx (xx.x)	xx (xx.x)	xx (xx.x)	xx (xx.x)	xx (xx.x)
Etc.	xx	xx (xx.x)	xx (xx.x)	xx (xx.x)	xx (xx.x)	xx (xx.x)	xx (xx.x)

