 Patients with ER+ and PR+
 (N=xxx)

 Patients with ER+ and PR-
 (N=xxx)

[figure not shown]
 Patients with ER- and PR+
 (N=xxx)

Table S4.8.1.1 Best Overall Response Rate - Full Analysis Set

Table S4.8.2.1 Duration of Clinical Response - Full Analysis Set

Table S4.8.3.1 Progression-Free Survival - Full Analysis Set

Figure 1.1 Progression-Free Survival, Asian vs. Non-Asian - Full Analysis Set

[figure not shown]
Note that this figure is an example. The outputs are not real/correct, these were invented.

The following figures will be created using the same layout as Figure 1.1.

Figure 1.2 Progression-Free Survival, Asian vs. Non-Asian - Per Protocol Set

Figure 2.1 Time to Deterioration of ECOG Performance Status, Asian vs. Non-Asian - Full Analysis Set

The following figures will be created using the same layout as Figure 2.1.

Figure 2.2 Time to Deterioration of ECOG Performance Status, Asian vs. Non-Asian - Per Protocol Set

Figure 3.1 Cumulative Incidence Estimates for Time to Stomatitis Grade 2-4, Asian vs. Non-Asian - Safety Set

Figure 3.2 Cumulative Incidence Estimates for Time to Rash Grade 2-4, Asian vs. Non-Asian - Safety Set

Figure 3.3 Cumulative Incidence Estimates for Time to Infections Grade 2-4, Asian vs. Non-Asian - Safety Set

Figure 3.4 Cumulative Incidence Estimates for Time to Pneumonitis Grade 2-4, Asian vs. Non-Asian - Safety Set

[figure not shown]

Listing 1.1 Disposition: Analysis Populations

Country	Site ID	Patient ID	Screen Failure/ Reason for Screen Fail	Screening Date	Informed Consent Date	Eligibility	Full Analysis Set/ Per Protocol Set/ Safety Set	Discontinuation of Study Drug/ Reason	Last Date in Study/ Days in Study
xxx	xxx	xxxx	xxx/xxx	DD-MMM-YYYY	DD-MMM-YYYY	Y	xxx/xxx/xx	xxxx/xxx	DD-MMM-YYYY

Generated with data from all patients, sorted by Site ID and Patient ID

Programmer note: the response to the column Full Analysis Set/Per Protocol Set/Safety Set is Y/N to each of these three sets, e.g., Y/Y/N. Y=Yes, N=No

Listing 1.2 Disposition: End of Study Treatment and Study Evaluation Completion

[figure not shown]
Page 1 of Listing

Country	Site ID	Patient ID/ FAS/ PPS/ SS	Last Known Date Patient Took Study Drug	Primary Reason for End of Study Treatment	Specify Reason for End of Study Treatment	Principal Cause of Deathh	If Other Cause, Specify Cause of Death	Date of Death	Patient Agrees to be Followed for Post- Treatment Evaluations
			DD-MMM-YYYY	XXXX	XXXX	XXXX	XXXX	DD-MMM-YYYY	Y

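### SAP Figures 3.1–3.4 promise cumulative incidence, but the only estimator the plan names is Kaplan-Meier and no censoring rule is given; if exits from the counting window are censored, the absolute risk is overstated

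*SAP*

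**What the plan says.** The SAP lists four curves by Asian and Non-Asian group on the Safety Set. The first is "Figure 3.1 Cumulative Incidence Estimates for Time to Stomatitis Grade 2-4, Asian vs. Non-Asian - Safety Set"; Figures 3.2–3.4 repeat the title for rash, infections and pneumonitis. The text beside them is a layout instruction, "The following figures will be created using the same layout as Figure 2.1". Figure 2.1 is the time-to-ECOG-deterioration curve, and the companion Table 7.3.1 uses Kaplan-Meier estimates. The figure images are not available.

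Protocol section 10.2 sets the general rule: "Time to event data including rates of affected patients will be assessed using the Kaplan-Meier method". No supplied text exempts adverse-event onset from it or mentions competing events.

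The matching table is "Table 6.18 Time to onset of Treatment-Emergent Adverse Event of Special Interest Associated with mTOR Inhibition, Grade 2-4 - Safety Set". It borrows the layout of Table 6.14, whose footnote reads "Median time to resolution based on Kaplan-Meier Estimates".

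The counting window is explicit. The SAP footnotes count events with a start date on or after the "date of the first dose of study drug and within 30 days of treatment discontinuation". Protocol section 10.5 says the same from the other side: "AE starting more than 30 days after discontinuation of study drug will not be considered as treatment-emergent". Protocol section 6.1.4 ends treatment at progression, unacceptable toxicity, death, consent withdrawal or any other discontinuation.

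**The concern.** Cumulative incidence means the proportion of treated patients who have had the event by a given time. Kaplan-Meier assumes that a censored patient can still have the event later, at the same rate as those who remain under observation. That assumption does not fit an endpoint that closes 30 days after treatment stops. Once a patient has died, or her window has closed without the event, her contribution is settled: no event. Censoring her gives her share of the risk to the patients still on treatment, so the curve rises too high for its title.

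The ECOG curve whose layout is reused does not have this problem for death, because Table 7.3.1 counts death from any cause as deterioration. The adverse-event curves have no such rule.

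At stake is the accuracy of curves for four listed events of special interest (protocol section 8.1.3), which serve the primary safety objective. A reader would take the height of a curve with this title as the chance of the toxicity.

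**Working it through.** **Stated figure.** The documents give no one-year risk for these events, so there is none to reproduce. The check compares the two estimators under stated assumptions.

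**Inputs from the protocol**
- Grade 2–4 rates, summed from the combination arm of Table 1-1: stomatitis 22 + 8 + 0 = 30%; rash 9 + 1 + 0 = 10%; pneumonitis 6 + 3 + 0 = 9%. Table 1-1 has no pooled infection row, so infections cannot be computed.
- Final median PFS of 7.82 months in the same trial (section 1.2.1.2.2), which is 34 weeks.
- Window of 30 days after discontinuation: d = 30/7 = 4.29 weeks.

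**Assumptions**
- Time to end of treatment is exponential with median 34 weeks: μ = ln 2 / 34 = 0.02039 per week.
- Onset is independent of end of treatment. Its hazard is either constant or early (Weibull, shape 0.5).
- The hazard is calibrated so that the eventual counted incidence equals the Table 1-1 rate.
- Kaplan-Meier censors at the end of the window.

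**Formulas.** Let H(t) be the cumulative onset hazard, h(t) its derivative, and G(t) the probability of still being in the window: 1 for t ≤ d, then exp(−μ(t − d)).
- Kaplan-Meier complement: 1 − exp(−H(50)).
- Cumulative incidence: ∫ from 0 to 50 of h(t) exp(−H(t)) G(t) dt.

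**Stomatitis, constant hazard**
- Calibration: exp(−λd) × μ/(μ + λ) = 0.70 gives λ = 0.00778 per week. Check: 0.967 × 0.724 = 0.700.
- Kaplan-Meier complement: 1 − exp(−0.00778 × 50) = 32.2%.
- Cumulative incidence: (1 − exp(−λd)) + exp(−λd) × λ/(λ + μ) × (1 − exp(−(λ + μ)(50 − d))) = 0.0328 + 0.967 × 0.276 × 0.724 = 22.6%.

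**Results at week 50**

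| Event | Onset hazard | 1 − KM | Cumulative incidence | Gap (points) |
|---|---|---|---|---|
| Stomatitis | constant | 32.2% | 22.6% | 9.6 |
| Stomatitis | early | 32.5% | 26.5% | 6.0 |
| Rash | constant | 9.8% | 6.7% | 3.1 |
| Rash | early | 10.7% | 8.6% | 2.1 |
| Pneumonitis | constant | 8.8% | 6.0% | 2.8 |
| Pneumonitis | early | 9.6% | 7.7% | 1.9 |

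**Sensitivity to exit speed.** With the interim median PFS of 6.93 months (about 30 weeks), the stomatitis gap is 11.4 points (constant) or 6.8 points (early).

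**Sensitivity to onset timing.** If all stomatitis starts in the first three months, calibrated to 30% with median PFS 7.82 months, the 12-month comparison is 33.8% against 30.0% with exits from day 0, and 31.6% against 30.0% with exits from month 1. If all starts in the first two months and exits begin at month 1, it is 30.5% against 30.0%.

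**Scale against sampling error.** The documents give 198 patients enrolled by mid-2014 and a maximum of 400, with no Asian/Non-Asian split. For the 9.6-point gap, the standard error √(0.226 × 0.774/n) is 5.9 points at n = 50 (a ratio of 1.6) and 2.1 points at n = 400 (a ratio of 4.6). The ratio depends so much on an unknown n that percentage points are the better measure.

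**The case against.** The strongest objection is that Kaplan-Meier is inferred here. Section 10.2 is a general sentence that does not mention adverse-event onset. A layout instruction concerns appearance. The Table 6.14 footnote concerns time to resolution. Outputs that are clearly Kaplan-Meier, such as Tables 7.3.1 and 8.3.1, are labelled as event-free probabilities, so a different label may signal a different estimator. The supplied SAP text consists of output shells, and a methods text may exist elsewhere. All of this stands. It means the plan cannot be said to have chosen a biased estimator. It also means that a programmer working from these documents has only Kaplan-Meier to follow.

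A second objection is that one minus Kaplan-Meier answers a legitimate question about the onset rate while on treatment. That is true, but it is not what the titles promise.

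Four stronger readings are tempting and are not supported:
- **A Kaplan-Meier contrast between Asian and Non-Asian patients depends on how fast each group progresses.** Under independent exits it does not. With the same stomatitis onset hazard and median treatment of 34 or 26 weeks, one minus Kaplan-Meier at week 50 is 32.2% in both cases, while the cumulative incidence is 22.6% and 20.6%.
- **These are the only time-based displays of the toxicities.** Tables 6.18 and 6.18.1 cover time to onset, and Tables 6.14–6.17.1 cover time to resolution.
- **The curves must lie above Tables 6.13–6.13E.** None of those tables uses grades 2–4, and the modelled rash curve (9.8% at week 50, constant hazard) is below even the crude 10%.
- **Progression makes the event impossible.** Only death does. After progression, it is the counting window that excludes later events.

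**Conclusion.** The point holds as a gap in specification with a known direction of error. The titles promise cumulative incidence, the only method named is Kaplan-Meier, and the handling of death and of event-free exit from the window is not stated. If those exits are censored, the curves overstate absolute risk in every scenario examined. If such patients are instead kept at risk to the end of follow-up, this bias disappears.

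Under the exponential model with a 34-week median, the week-50 overstatement is about 6 to 10 points for stomatitis and 2 to 3 points for rash and pneumonitis. It shrinks towards zero if onset falls almost entirely in the first two to three months. The documents do not give the onset timing, and the rates and exit speed are carried over from the earlier trial.

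Severity is modest. Protocol section 10.7 rules out hypothesis testing, section 10.5 bases the safety assessment mainly on adverse-event frequencies, and the SAP tabulates crude incidences.

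**What to change.** For SAP Figures 3.1–3.4 and the onset analysis in Tables 6.18 and 6.18.1:
- State the Aalen-Johansen cumulative incidence function as the estimator.
- Define two competing events: death, and the end of the at-risk window (end of treatment plus 30 days) without the adverse event.
- Censor only administrative ends: data cut-off, country closure and switch to commercial drug.
- Exempt adverse-event onset from the Kaplan-Meier sentence in protocol section 10.2, or record the exception in the SAP.

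The cost is a few lines of text and a programming option. Listing 1.2 already carries the last-dose date, the reason for stopping and the date of death.

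There is one drawback. The curves will then show absolute on-study risk, so the Asian/Non-Asian contrast will partly reflect differences in treatment duration. A note beside each figure should say so.
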